### **6.8.2. Physical Examination**

A complete physical examination should include source documentation of general appearance, and the following body systems: head, neck, and thyroid; eyes, ears, nose, throat, mouth, and tongue; chest (excluding breasts); respiratory; cardiovascular; lymph nodes; abdomen; skin, hair, nails; musculoskeletal; neurological.

The focus of a symptom driven physical examination will be determined by the investigator based on subject complaint. For example, if a subject complains of a cough, a lung exam should be performed. If consistent with pneumonia (rales/crackles on exam) then an AE would be documented.

Height, body weight, and hip circumference will be collected at specified time points.

### **6.8.3. Vital Signs**

Assessment of vital signs will include measurement of resting blood pressure, pulse, respiratory rate and temperature.

Blood pressure will be measured using the following standardized process:

- Subject should sit for  $\geq 5$  minutes with feet flat on the floor and measurement arm supported so that the midpoint of the manometer cuff is at heart level;
- Use a mercury sphygmomanometer or automatic blood pressure device with an appropriately sized cuff with the bladder centered over the brachial artery;

Measure and record the blood pressure to the nearest 2 mmHg mark on the manometer or to the nearest whole number on an automatic device.

#### **6.8.4. Medical History**

Medical history, including details regarding illnesses and allergies, date(s) of onset, and whether condition(s) is currently ongoing, and medication history will be collected on all subjects during Screening. If available, historical liver biopsy information will also be collected.

#### **6.8.5. Pharmacogenomic Testing**

From subjects who agree to participate and provide consent, one blood sample will be obtained. This sample should be collected at the Day 1 visit, but may be collected at any time during the study or at a separate poststudy visit, if necessary.

#### **6.8.6. Health Related Quality of Life (HRQoL)**

It is recommended that these questionnaires be completed prior to the clinical and laboratory assessments. The subject should read the questionnaires by himself/herself and record the answers by himself/herself.

##### **6.8.6.1. SF-36 Health Survey**

The SF-36 Health Survey asks 36 questions to measure functional health and well-being from the subject's point of view and consists of eight health domains (physical functioning, role-physical, bodily pain, general health, vitality, social functioning, role-emotional, and mental health). These health domain scales contribute to the physical health and mental health summary measures.

##### **6.8.6.2. CLDQ**

The CLDQ asks 29 questions related to liver disease to measure health related quality of life in subjects with chronic liver disease.

##### **6.8.6.3. WPAI**

The Work Productivity and Activity Impairment (WPAI) questionnaire asks 6 questions regarding the effect of NASH on a person's ability to work and perform regular activities.

#### **6.8.7. Electrocardiogram**

Standard 12-lead electrocardiogram (ECG) assessments will be performed. The Investigator will review the ECGs for any clinically significant abnormalities to ensure subject safety. Abnormal ECG findings that are considered clinically significant by the Investigator and meet the definition of an AE should be reported and recorded in the AE eCRF page.

#### **6.8.8. FibroScan®**

The sites will perform liver stiffness assessments by FibroScan®. It is required that each subject have the FibroScan® assessments done with the same type of probe at Baseline Day 1 and Week 12 visits (if available).

### **6.8.9. MRE and MRI-PDFF**

Liver stiffness will be assessed by MRE (shear wave 60 Hz) and the degree of steatosis will be measured by Magnetic Resonance Imaging - Proton Density Fat Fraction (MRI-PDFF). These assessments can occur sequentially.

The MRE and MRI-PDFF images will be analyzed by a central reader.

Please refer to the Study Reference Binder for MRE and MRI-PDFF imaging guidelines.

### **6.9. End of Study Definition**

Subjects are considered to have completed the study after the completion of the Week 16 Follow-Up visit, regardless of treatment duration or early termination of study drugs.

### **6.10. Poststudy Care**

No poststudy ongoing care will be provided.

### **6.11. Sample Storage**

Residual biological samples from all visits will be frozen and stored if specific consent is obtained. These stored samples may be used by Gilead or research partners of Gilead to help answer questions about the study drugs, NASH, and its associated conditions, or clinical laboratory testing to provide additional safety data. No human genetic testing will be performed without express consent of the study subjects. At the conclusion of this study, these samples may be retained in storage for Gilead for a period of up to 15 years.

## 7. ADVERSE EVENTS AND TOXICITY MANAGEMENT

### 7.1. Definitions of Adverse Events, Adverse Reactions, and Serious Adverse Events

#### 7.1.1. Adverse Events

An AE is any untoward medical occurrence in a clinical study subject administered a medicinal product, which does not necessarily have a causal relationship with the treatment. An AE can therefore be any unfavorable and/or unintended sign, symptom, or disease temporally associated with the use of a medicinal product, whether or not considered related to the medicinal product. AEs may also include pre- or posttreatment complications that occur as a result of protocol specified procedures, overdose, drug abuse/misuse reports, or occupational exposure. Preexisting events that increase in severity or change in nature during or as a consequence of participation in the clinical study will also be considered AEs.

An AE does not include the following:

- Medical or surgical procedures such as surgery, endoscopy, tooth extraction, and transfusion. The condition that led to the procedure may be an AE and must be reported.
- Preexisting diseases, conditions, or laboratory abnormalities present or detected before the Screening visit that do not worsen
- Situations where an untoward medical occurrence has not occurred (eg, hospitalization for elective surgery, social and/or convenience admissions)
- Overdose without clinical sequelae (see Section 7.6.1)
- Any medical condition or clinically significant laboratory abnormality with an onset date before the consent form is signed and not related to a protocol-associated procedure is not an AE. It is considered to be preexisting and should be documented on the medical history eCRF.

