### 6.3. Baseline/Day 1 Randomization and Assessments

Subjects returning to the clinic for randomization at Baseline/Day 1 should be instructed to fast (no food or drink, except water), starting from midnight (00:00) or earlier, as appropriate, on the evening prior to the Baseline/Day 1 visit to ensure an approximate 8-hour fast prior to the blood sample collection under fasting conditions the next morning.

After review of inclusion and exclusion criteria to confirm continued eligibility, subjects will be randomized to study drug assignment and receive their Subject Identification Number via the IWRS prior to their first dose of study drugs.

Randomization will be stratified by the presence or absence of diabetes mellitus as determined by medical history, use of medication for indication of diabetes mellitus, or based on Screening lab values if previously undiagnosed (ie, hemoglobin A1c  $\geq 6.5\%$  OR fasting plasma glucose  $\geq 126$  mg/dL).

The following will be performed and documented at the Baseline/Day 1 visit prior to dosing:

- QoL Questionnaires (SF-36, WPAI, and CLDQ)

Note: It is recommended that QoL questionnaires be completed prior to any study procedures being performed and prior to the subject seeing a health care provider.

- Symptom driven physical examination
- Record vital signs, waist circumference, and body weight
- Obtain blood samples for:
  - Chemistry
  - Hematology
  - Coagulation Panel
  - Lipid Profile
  - Hemoglobin A1c
  - Biomarkers
  - CCI
- Conduct standard 12-Lead ECG
- Perform FibroScan® (if available)
- Collect urine samples for:
  - Urine pregnancy test for females of child bearing potential only
  - Biomarkers
- Collect stool sample for Biomarkers (see Study Reference Binder for instructions)
- Dispense study drugs, and provide subject with instruction on appropriate dosing and administration; subject will take the Baseline/Day 1 dose of study drugs on-site
- Record all concomitant medications that the subject has taken since the previous visit
- Record any serious adverse events and all adverse events occurring since the Screening visit

Subjects will return to the investigative site at Week 1 ( $\pm 3$  days) for a mandatory safety visit. Then, starting at the Week 4 visit, subjects will have visits every 4 weeks up to the Week 12 visit.

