### **7.3. Investigator Requirements and Instructions for Reporting Adverse Events and Serious Adverse Events to Gilead**

After informed consent, but prior to initiation of study medication, the following types of events should be reported on the case report form (eCRF): all SAEs and AE related to protocol-mandated procedures.

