##### **8.6.2. Adverse Events**

Clinical and laboratory adverse events will be coded using the Medical Dictionary for Regulatory Activities (MedDRA). System Organ Class (SOC), High-Level Group Term (HLGT), High-Level Term (HLT), Preferred Term (PT), and Lower-Level Term (LLT) will be attached to the clinical database. Adverse event severity will be graded using the CTCAE Version 4.03.

Events will be summarized on the basis of the date of onset for the event. A treatment-emergent adverse event (TEAE) will be defined as 1 or both of the following:

- Any AEs with an onset date on or after the start date of study drugs and no later than 30 days after permanent discontinuation of study drug.
- Any AEs leading to premature discontinuation of study drugs.

Summaries (number and percentage of subjects) of TEAEs by SOC and PT will be provided. Treatment-emergent AEs will also be summarized by relationship to study drug and severity. In addition, TEAEs leading to premature discontinuation of study drug and study will be summarized and listed.

All AEs collected during the course of the study will be presented in data listings with a field for treatment-emergent event (yes/no).

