7.1.5. Treatment-Emergent Adverse Events

7.1.5.1. Definition of Treatment-Emergent Adverse Events

Treatment-emergent adverse events (TEAEs) are defined as 1 or both of the following:

- Any AEs with an onset date on or after the study drug start date and no later than 30 days after permanent discontinuation of study drug
- Any AEs leading to premature discontinuation of study drug.

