The CTCAE, Version 4.03 will be used to assign toxicity grades (0 to 4) to laboratory results for analysis. Grade 0 includes all values that do not meet the criteria for an abnormality of at least Grade 1. For laboratory tests with criteria for both increased and decreased levels, analyses for each direction (ie, increased, decreased) will be presented separately.

7.2.2.1. **Treatment-Emergent Laboratory Abnormalities**

Treatment-emergent laboratory abnormalities are defined as values that increase at least 1 toxicity grade from baseline at any postbaseline time point, up to and including the date of last dose of study drug plus 30 days for subjects who permanently discontinued study drug. If the relevant baseline laboratory value is missing, any abnormality of at least Grade 1 observed within the time frame specified above will be considered treatment emergent.

7.2.2.2. **Treatment-Emergent Marked Laboratory Abnormalities**

Treatment-emergent marked laboratory abnormalities are defined as values that increase from baseline by at least 3 toxicity grades at any postbaseline time point, up to and including the date of the last dose of study drug plus 30 days for subjects who permanently discontinued study drug. If the relevant baseline laboratory value is missing, any Grade 3 or 4 values observed within the timeframe specified above will be considered treatment-emergent marked abnormalities.

7.2.2.3. **Summaries of Laboratory Abnormalities**

Laboratory data that are categorical will be summarized using the number and percentage of subjects in the study with the given response at baseline and each scheduled postbaseline visit.

The following summaries (number and percentage of subjects) for treatment-emergent laboratory abnormalities will be provided by lab test and treatment group; subjects will be categorized according to the most severe postbaseline abnormality grade for a given lab test:

- Graded laboratory abnormalities

- Grade 3 or 4 laboratory abnormalities
- Marked laboratory abnormalities

For all summaries of laboratory abnormalities, the denominator is the number of subjects with nonmissing postbaseline values up to 30 days after last dosing date for the laboratory test of interest.

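### A pre-dose event that worsens on drug without stopping it can be missing from most AE tables, because the TEAE definition has no worsening limb and the pre-dose recording rules conflict

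*Protocol*

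**What the plan says.** **What is an AE.** Protocol 7.1.1 includes "Preexisting events that increase in severity or change in nature during or as a consequence of participation in the clinical study". Among its exclusions, the second removes preexisting conditions "present or detected before the Screening visit that do not worsen". The last says that a condition with an "onset date before the consent form is signed and not related to a protocol-associated procedure is not an AE", and sends it to the medical history form. That last exclusion makes no exception for worsening.

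**What is treatment-emergent.** SAP 7.1.5.1 has two limbs. The first is "Any AEs with an onset date on or after the study drug start date and no later than 30 days after permanent discontinuation". The second is any AE that causes the drug to be stopped early, whatever its onset. Protocol 8.6.2 has the same two limbs, the first beginning "Any AEs with an onset date on or after the start date of study drugs", and says that events are summarized by onset date.

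**What is tabulated.** The AE summaries in SAP 7.1.6 use treatment-emergent events. All deaths enter the high-level summary, and the AE listings are not restricted to treatment-emergent events. For laboratory data, SAP 7.2.2.1 uses a different principle: "values that increase at least 1 toxicity grade from baseline at any postbaseline time point".

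**What is recorded before dosing.** Protocol 7.3 limits AE entries between consent and first dose to "all SAEs and AE related to protocol-mandated procedures". Section 6.2.1 agrees and sends other occurrences to medical history. Section 6.3, in the list to be completed before the Day 1 dose, instead says: "Record any serious adverse events and all adverse events occurring since the Screening visit".

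**The concern.** Safety is the primary endpoint, and the AE part of it is reported through the TEAE tables. The protocol describes the main toxicities so far as gastrointestinal. Worsening of a symptom already present during a screening period of up to 6 weeks or longer is therefore a plausible form of drug effect. If such an event becomes Grade 3, serious or dose-interrupting on drug but keeps its earlier onset date, the tables meant to show it do not count it.

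The count also depends on data entry. With about 50 centers, the same clinical course can be a TEAE at one site and not at another, according to which section the site follows. The tables would not reveal this.

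**Working it through.** The plan states no figure on this point, so the check is to apply the rules to defined event types.

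**Inputs.** First dose is Day 1. Last dose is taken as Day 84 (an assumption: 12 weeks × 7 days), so the window closes at 84 + 30 = Day 114.

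- Current rule: treatment-emergent if 1 ≤ onset day ≤ 114, or if the AE stops the drug.
- Rule with a worsening limb: as above, or if the AE has a pre-dose onset and worsens on a day from 1 to 114.

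| Event | Current rule | With worsening limb |
|---|---|---|
| New on drug, Day 20 | TEAE | TEAE |
| Onset Day −10, worsens Day 20, original onset kept | not TEAE | TEAE |
| Same course, re-entered with onset Day 20 | TEAE | TEAE |
| Onset Day −10, worsens, drug stopped | TEAE | TEAE |
| Onset Day −10, no worsening | not TEAE | not TEAE |

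Only the second row changes. Rows 2 and 3 are the same clinical course, separated only by the onset date that the site enters. Protocol 7.3.1.1 requires all AEs after first dose to be reported, but neither document says which onset date a worsened event should carry.

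**How a site reaches row 2 or row 3.**

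- A site following 6.2.1 and 7.3 has no AE record for an ordinary pre-dose symptom. When the symptom worsens, the natural entry is a new AE with an on-drug date: row 3, counted.
- A site following 6.3 already holds an AE record with a pre-dose onset. If it updates that record: row 2, not counted.
- Pre-dose SAEs and procedure-related AEs are AE records under every version of the rule, so row 2 is open to them at any site.
- A site applying the last exclusion of 7.1.1 literally to a pre-consent condition makes no AE entry when it worsens. The event then stays in medical history, which SAP 5.3 leaves uncoded and only lists. A worsening limb alone would not recover it.

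**Where a row 2 event goes missing.** It is absent from the overall TEAE, treatment-related, Grade 2+, Grade 3+, SAE and interruption tables in SAP 7.1.6. It remains in the listing of all AEs, flagged as not treatment-emergent, and in the grade, SAE and interruption listings where it qualifies.

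**Scale.** No rate of such events is given. The effect per subject follows from the planned arm sizes: 1/50 = 2 percentage points of incidence in each active arm, and 1/25 = 4 points on placebo.

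**The case against.** The strongest reply is that the protocol's main rules already lead to the right answer. Sections 6.2.1 and 7.3 both keep ordinary pre-dose events off the AE form, and 7.1.1 makes worsening an AE. A worsened symptom therefore first appears as an AE with an on-drug date and meets the onset limb. The 6.3 wording is one line in a visit checklist, placed after the line about the on-site dose, and 6.2.1 covers the whole period to first dose and refers to Section 7. The last exclusion in 7.1.1 can be read as describing the condition as it stood at consent. Entry details are left to eCRF completion guidelines, which are not in these documents.

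Much of this stands. The loss is not automatic, and divergent practice is possible rather than shown. Incomplete onset dates also lean toward inclusion under SAP 7.1.5.2. But the checklist line contradicts the other two sections as written, the definition has no worsening limb, and nothing in either document fixes the onset date of a worsened event.

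A reader might infer that treatment emergence rests on onset date alone, or that such events vanish from every safety table. Neither is so. The discontinuation limb ignores onset, all deaths are counted, laboratory tables use grade change from baseline, and the AE listings are unrestricted.

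**Conclusion.** The point holds as a gap in the definition combined with inconsistent recording rules. It affects non-laboratory AEs that carry a pre-dose onset, worsen on drug and do not lead to permanent discontinuation. For these, the main AE tables can undercount, and whether they do depends on site entry.

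The size is unknown. A reader might be tempted to take the Phase 1 multiple-dose rates (nausea 33%, diarrhea 21%) and apply assumed shares of preexisting symptoms to obtain a percentage dilution. The documents do not support that. Those rates come from healthy adults on 100 to 200 mg daily, against 5 and 20 mg here, and nothing gives the share of events with a milder pre-dose form or the share entered under the original date. A claim that the contrast with placebo shrinks by a fixed factor would also need those shares to be equal across arms. No attenuation figure should be stated.

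The conclusion rests on the text of the two documents and assumes that the eCRF completion guidelines do not already settle the onset-date question.

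**What to change.** 1. Reconcile protocol 6.3 with 6.2.1 and 7.3, so that all sites record pre-dose events in the same way.
2. Add *unless it worsens* to the last exclusion in protocol 7.1.1.
3. State in the protocol and eCRF guidelines that a preexisting condition or pre-dose AE that worsens after first dose is entered as a new AE, with the date of worsening as its onset.
4. Add a limb to protocol 8.6.2 and SAP 7.1.5.1 for AEs with pre-dose onset that rise in CTCAE grade or become serious between first dose and 30 days after last dose.

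Items 3 and 4 belong together. The new limb can act only on AE records with a known grade and date of worsening. Medical history as described in protocol 6.8.4 has onset dates and ongoing status but no CTCAE grade. Double counting is not a concern in the subject-level tables, because SAP 7.1.6 counts a subject once per summary.

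The cost is a small eCRF-guideline change to capture the date and grade of worsening, and slightly more events counted in all arms. No extra visits or assessments are needed.

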#### 7.1.2. Serious Adverse Events

A **serious adverse event** (SAE) is defined as an event that, at any dose, results in the following:

- Death
- Life-threatening (Note: The term “life-threatening” in the definition of “serious” refers to an event in which the subject was at risk of death at the time of the event; it does not refer to an event that hypothetically might have caused death if it were more severe.)
- In-patient hospitalization or prolongation of existing hospitalization
- Persistent or significant disability/incapacity
- A congenital anomaly/birth defect

A medically important event or reaction: such events may not be immediately life-threatening or result in death or hospitalization but may jeopardize the subject or may require intervention to prevent one of the other outcomes constituting SAEs. Medical and scientific judgment must be exercised to determine whether such an event is a reportable under expedited reporting rules. Examples of medically important events include intensive treatment in an emergency room or at home for allergic bronchospasm; blood dyscrasias or convulsions that do not result in hospitalization; and development of drug dependency or drug abuse. For the avoidance of doubt, infections resulting from contaminated medicinal product will be considered a medically important event and subject to expedited reporting requirements.

### **7.1.3. Clinical Laboratory Abnormalities and Other Abnormal Assessments as Adverse Events or Serious Adverse Events**

Laboratory abnormalities without clinical significance are not recorded as AEs or SAEs. However, laboratory abnormalities (eg, clinical chemistry, hematology, and urinalysis) that require medical or surgical intervention or lead to study drug interruption, modification, or discontinuation must be recorded as an AE, as well as an SAE, if applicable. In addition, laboratory or other abnormal assessments (eg, electrocardiogram, x-rays, vital signs) that are associated with signs and/or symptoms must be recorded as an AE or SAE if they meet the definition of an AE or SAE as described in Sections 7.1.1 and 7.1.2 respectively. If the laboratory abnormality is part of a syndrome, record the syndrome or diagnosis (eg, anemia), not the laboratory result (ie, decreased hemoglobin).

